5.2.1 Dose Limiting Toxicity

A DLT is defined as the occurrence within the first 4 weeks following a single administration of *hMaxi-K* of an unacceptable toxicity, as described below. Adverse events for cardiovascular, blood chemistry, complete blood count, or urine categories of adverse events will be graded according to the criteria provided in [Appendix A](#).

No acute toxicity was seen in the preclinical studies with administered doses up to 1000 μg (approximately 1500 $\mu\text{g}/\text{kg}$) or in men and women given doses up to 16000 μg . Potential toxicities would be those that could occur due to enhanced efflux of K^+ with resultant decreased intracellular Ca^{++} concentration thus altering smooth muscle function in diverse organ systems.

The following criteria will be used to define:

DLT:

- 1) Any adverse events of Grade 2 or higher in the cardiovascular category of adverse event criteria listed in [Appendix A](#);
- 2) Any adverse events of Grade 2 or higher in the blood chemistry, complete blood count, or urine categories of adverse event criteria listed in [Appendix A](#).

- 3) Penile pain and/or erection that persists for more than four hours after gene transfer;
- 4) Change in random hormone levels greater than 2 times the upper or lower limits of normal at any time post dosing..

Stopping Rule

If within 4 weeks following the single administration of *h*Maxi-K, if any participant experiences a grade 3 or higher dose limiting toxicity, no additional participants will be accrued and no further doses of *h*Maxi-K (or placebo) will be administered. Clinical data regarding the event will be collected, reviewed, and discussed with the Ethics Committee (EC) and Kuwait Ministry of Health (MOH). After review of these data with EC and MOH the clinical study may resume only with concurrence of EC and MOH.

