4.1 Inclusion Criteria

Eligible participants must meet the following inclusion criteria:

- a) Signed Informed Consent
- b) Be adult males over 18 years of age diagnosed with erectile dysfunction and whose ED is attributable to an underlying, stable medical condition such as hypertension and

atherosclerosis, antihypertensive medication, type I and type II diabetes mellitus, pelvic surgery and pelvic radiation, cerebrovascular accidents (stroke), multiple sclerosis, and Parkinson's disease;

- c) Participants must have been unable to have successful sexual intercourse for 3 months prior to study entry without specific ED therapy such as Vacuum Erection device (VED), Viagra™ (sildenafil), Cialis™ (tadalafil), Muse™ (alprostadiol), or intracavernous injection therapy with an erectile function domain score of IIEF >10 and < 21 at screening and baseline;
- d) Have been unable to tolerate, do not wish to continue, or have had unsuccessful results with, prior therapy for ED, e.g., Viagra™, intracavernous injection therapy, Muse™, or VED;
- e) If diabetic, documentation of HgA_{1c} less than or equal to 8.5 % prior to enrollment;
- f) If receiving medication for hypertension, documentation of blood pressure has been stable on the same medication for at least 2 months prior to enrollment;
- g) Be heterosexual and in a stable, monogamous relationship of at least six months duration;
- h) Agree to attempt intercourse with their partner at least four times per month while participating in the study;
- i) Agree not to use other treatments for ED while participating in this study;
- k) Have screening laboratory values and ECG that are within the normal range. See exclusion criterion below.
- l) Have a normal physical examination of the penis;
- m) If participant had a radical prostatectomy a PSA <0.4 for at least one year documented by 2 measurements during the preceding year;
- n) Be literate, able to give written informed consent, and comply with all study procedures and requirements.

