4.2 Exclusion Criteria

Participants will be excluded who have:

- a) A history of sickle-cell disease, sickle cell trait, or any other medical condition that, in the judgment of the investigator, would contraindicate the administration of study medication or interfere with the study evaluations;
- b) In the judgment of the investigator any condition that would interfere with participation in the study (including geographical inaccessibility), that would contraindicate the administration of study medication or interfere with the study evaluations.
- c) Had within six months prior to enrollment any of the following:
 - Myocardial infarction
 - Cerebrovascular accident
 - Uncontrolled hypertension (systolic >160 or diastolic >100mmHg)
 - Arrhythmia
 - Congestive heart failure (dyspnea on minimal exertion or while supine)

- Unstable angina (chest pain greater than three times weekly while on therapy)
- Required treatment with calcium channel, beta-blocker medication/nitrates, or anti-epileptic drugs for less than 6 months at the time of randomization

d) Poorly controlled diabetes mellitus as defined by HgA_{1c} > 8.5 mg% at time of enrollment;

e) Change in medication for diabetes or hypertension within 2 months of study enrollment;

f) Gonadal failure (testosterone < 200 ng/dl) not treated with hormone replacement;

g) History of malignancy except non-melanomatous skin cancers

h) A life expectancy of less than 12 months;

i) An indwelling urethral catheter;

j) A prior penile prosthetic implant

l) Received an investigational drug, investigational therapy, or other form of ED therapy, including approved treatments, within the past 30 days;

m) Peyronie's disease;

n) Any screening laboratory values outside of the normal laboratory range as defined by the central laboratory normal ranges and in the judgment of the investigator is considered clinically significant (hepatic biochemical markers [AST, ALT, GGT, alkaline phosphatase, and bilirubin] > twice the upper limit of the normal reference range may be accepted with written consent of the sponsor).

o) Any clinically significant ECG abnormality

NOTE: Sinus bradycardia of 50-59 bpm is permissible. Other abnormalities that can be normal variants (and considered clinically insignificant) may be permissible. However, participants with such abnormalities cannot be randomized without review of their medical history and prior written approval of the sponsor (or designee).

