If a clinically serious sign or symptom is reported the medical monitor will contact the sponsor and no further enrollment will be done until the medical monitor or sponsor gives permission. In the previously completed clinical study evaluating intracorporal administration of up to 16000 μg *hMaxi-K* in 20 participants with ED, there was only one adverse event considered possibly related to *hMaxi-K* ("tingling warmth in the glans").

To minimize the possibility of dehydration and/or a vasovagal response following injection of the *hMaxi-K*, participants will be instructed to eat breakfast and drink fluids on that morning.

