6.6 Laboratory Safety Tests and Pharmacokinetics Evaluations

An accredited laboratory will function as the central laboratory for all plasma and urine specimens.

Laboratory safety tests will be performed as follows. The laboratory safety tests include:

- Hematology: Complete blood count (CBC) with differential: Screening (V1), Week 1 (V 3), Week 4 (V4), 12 weeks (V6) and 24 weeks (V7) post dosing with study drug.
- Platelet count, PT, PTT, sedimentation rate (sed. rate), CRP only at Visits 1, 3 and 7 only.
- Chemistry: Blood Urea Nitrogen (BUN), creatinine, electrolytes (Na⁺, K⁺, Mg⁺⁺, Ca⁺⁺, CO₂, Cl), albumin, alkaline phosphatase, ALT, AST, LDH, GGT, total bilirubin, total protein, glucose at Screening (V1), Week 1 (V3) , Week 4 (V4), 12 weeks (V7) and 24 weeks (V7) post dosing with study drug.
- Urinalysis: Microscopic RBC and WBC, protein, glucose, nitrites, and specific gravity at Screening (V1), Week 1 (V 3), Week 4 (V4), 12 weeks (V6) and 24 weeks (V7) post dosing with study drug.
- Endocrine: Total testosterone, random cortisol, TSH, T4 (V1, V3, and V7 only);
- At screening visit only, participants must have a hemoglobin A1c
- At V2 –V7, plasma specimens will be collected to assay for the presence of *hSlo* DNA by PCR. These will be kept frozen at -20° C or less at the site for eventual assay

by Sponsor. At Visit 2 specimens should be collected both pre-dosing (to serve as a baseline) and 2 hours post-dosing

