9.0 Adverse Events Definitions and Monitoring

9.1 Adverse Event

An adverse event is any unfavorable and unintended diagnosis, symptom, sign (including an abnormal laboratory finding), syndrome or disease which either occurs during the study, having been absent at baseline, or, if present at baseline, appears to worsen.

A treatment emergent adverse event (TEAE) will be considered an event that is temporally associated with the use of the study drug, whether or not considered related to the study drug.

Examples of AEs are as follows:

- Changes in the general condition of the participant
- Subjective symptoms offered by or elicited from the participant
- Objective signs observed by the Investigator or other study personnel
- All concurrent diseases that occur after the start of the study, including any change in severity or frequency of preexisting disease
- All clinically relevant abnormalities in laboratory values or clinically relevant physical findings that occur during the study.

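### As literally written, hormone DLT criterion 4 cannot register a fall from a baseline at or below twice the lower limit of normal, and its timing contradicts the 4-week DLT definition

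*Protocol*

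**What the plan says.** Protocol Section 5.2.1 opens by fixing a window: "A DLT is defined as the occurrence within the first 4 weeks following a single administration of" the study product. Four criteria follow. The first two use Appendix A grades, the third concerns penile pain or erection lasting beyond four hours, and the fourth is the hormone rule: "Change in random hormone levels greater than 2 times the upper or lower limits of normal at any time post dosing". The stopping rule in the same section carries its own 4-week limit and a grade threshold: "if any participant experiences a grade 3 or higher dose limiting toxicity, no additional participants will be accrued".

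Other parts of the plan that bear on the criterion:

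- **Sampling.** Section 6.6 lists "Endocrine: Total testosterone, random cortisol, TSH, T4 (V1, V3, and V7 only". V1 is screening, V3 is Week 1, and V7 is Week 24 or exit.
- **Entry.** Inclusion k requires that men "Have screening laboratory values and ECG that are within the normal range". Exclusion n removes men with out-of-range values that the investigator judges clinically significant, the ranges being "as defined by the central laboratory normal ranges".
- **Grading.** Appendix A has hematology, chemistry, urinalysis and cardiovascular sections, and no hormone rows. Events not listed there are graded on the general scale in Section 9.4.
- **Reporting.** Section 9.5 requires adverse events that meet the four criteria to reach the sponsor within 24 hours.
- **Analysis.** SAP Section 9.4 tabulates adverse events by DLT without defining the term. SAP Section 6 defines change, for laboratory data, as the post-baseline value minus the baseline value.

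**The concern.** Criterion 4 compares a change with a multiple of a reference limit. On the high side that gives a strict but reachable rule. On the low side it does not work: a hormone level cannot go below zero, so a large part of the normal range may lie where no fall, however complete, is big enough. The same rule can also flag movements that begin and end inside the normal range. It is the only hormone limit in either document, so nothing else corrects it.

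The second problem is timing. The lead sentence limits a DLT to the first 4 weeks, while criterion 4 runs for as long as the participant is followed. Only two hormone draws are scheduled after dosing, and one of them is far outside 4 weeks.

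At stake are which events are counted as DLTs in the SAP tables, which are sent to the sponsor within 24 hours and, for events graded 3 or higher, whether accrual stops.

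**Working it through.** The plan states no figure for this rule, so there is nothing to reproduce. The check is a bound, followed by a comparison of dates.

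**Inputs.** Criterion 4 and the 4-week window come from Protocol Section 5.2.1, the draw schedule from Section 6.6, and the definition of change from SAP Section 6. The documents give no hormone reference ranges, so R = ULN/LLN is an assumption, shown over a range.

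**Low side.** Work in units of LLN, with baseline B and post-dose value P ≥ 0. The criterion needs B − P > 2. The largest possible value of B − P is B, reached at P = 0. The low side can therefore be met by a fall only if B > 2, and then only if P < B − 2.

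| Baseline B | Largest possible fall | P must be below | Fall needed |
|---|---|---|---|
| 1.0 | 1.0 | impossible | – |
| 1.5 | 1.5 | impossible | – |
| 2.0 | 2.0 (not above 2) | impossible | – |
| 2.01 | 2.01 | 0.01 | 99.5% |
| 2.5 | 2.5 | 0.5 | 80% |
| 3.0 | 3.0 | 1.0 | 66.7% |
| 4.0 | 4.0 | 2.0 | 50% |

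**Misclassified cases.**

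- 1.8 to 0.1: change 1.7, a fall of 1.7/1.8 = 94%. Not a DLT.
- 4.0 to 1.9: change 2.1. A DLT, although the value is still above LLN.
- 1.5 to 3.6: change 2.1. Because the criterion gives no direction, this rise also meets the words, and it stays within the normal range if R is 3.6 or more.

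**Width of the unreachable band.** The normal range runs from 1 to R. The part at or below 2 has width min(2, R) − 1, so its share is 1/(R − 1) for R ≥ 2, and 100% for R below 2.

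| Assumed R | 2 | 2.5 | 3 | 4 | 5 | 10 |
|---|---|---|---|---|---|---|
| Share of range width | 100% | 67% | 50% | 33% | 25% | 11% |

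These are shares of the width of the range, not of participants. Any baseline below LLN, which exclusion n allows when it is not clinically significant, is also in the band. For testosterone, an assumed LLN of 200 to 350 ng/dl would put every baseline at or below 400 to 700 ng/dl in it. The 200 ng/dl in exclusion f is an eligibility cut-off and is not stated to be the LLN.

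**Window.** The scheduled post-dose hormone draws are Week 1 (inside 4 weeks) and Week 24 (outside). A qualifying result at Week 24 satisfies criterion 4 and fails the lead sentence, so 1 of the 2 draws has no settled DLT status.

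**The case against.** The strongest reply is that criterion 4 was meant as a level rule: above twice the upper limit, or below half the lower limit. Appendix A supports this, because its multiples of ULN grade the measured value and not a difference from baseline. The SAP definition of change is an analysis convention and is not said to govern DLTs. This stands as the likely intent. It does not rescue the text, because neither document says it, and two careful readers could classify the same Week 1 result differently.

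A reader might infer that men with low-normal baselines can never meet the low side at all. That goes too far. The word change carries no direction, so a rise of more than 2 × LLN meets it literally, and on the level reading the impossibility disappears. What holds is narrower: read as a difference, no fall can qualify from those baselines. Allowing rises does not help the rule, since it then flags a rise to 3.6 × LLN and misses near-total loss.

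A reader might also infer that the stopping rule is disabled or that hormone toxicity would go unseen. The documents do not support either:

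- Stopping needs grade 3 or higher. Without an Appendix A row, that means the incapacitating symptoms described in Section 9.4, which a clinically silent fall is unlikely to reach. Stopping also has its own 4-week limit, so the window conflict does not alter accrual.
- Adverse events already include "All clinically relevant abnormalities in laboratory values or clinically relevant physical findings that occur during the study" (Section 9.1). Section 9.5 gives serious events their own 24-hour report and asks the investigator to pass on findings that suggest significant hazards, with no deadline attached.
- Section 5.2 adds a separate pause to enrollment: "If a clinically serious sign or symptom is reported the medical monitor will contact the sponsor".
- SAP Section 9.4 flags every laboratory result as high, low or normal, with shift tables, so no hormone data are lost.
- This is a parallel, single-injection trial, so no dose escalation depends on a DLT.

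Finally, the two time phrases could be read as nested, with the 4-week limit applying throughout. Equally, the open-ended wording may be deliberate, since Section 1.1 cites an effect lasting at least six months in rats. The text does not choose.

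**Conclusion.** The point holds for the literal wording. Read as a difference from baseline, criterion 4 excludes every fall from a baseline at or below 2 × LLN and admits some changes that may stay within the normal range. The bound needs no outside data. Its extent does: 11% to 100% of the range width for assumed R of 10 down to 2. No event rate is claimed.

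The residual gap is a marked hormone fall that is an adverse event but is neither serious nor clinically obvious. It would be left out of the DLT table and the 24-hour report, and would affect stopping only if graded 3 or higher under Section 9.4.

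The window contradiction is real but secondary. It certainly affects the DLT count. Its effect on the 24-hour report is arguable: Section 9.5 points to the criteria, and criterion 4's own wording covers Week 24, but a reader could carry the 4-week limit across. The change is worth making because it is cheap and concerns a safety definition; it does not put the trial's conduct in doubt.

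**What to change.** 1. Replace criterion 4 with: *a post-dose hormone value > 2 × ULN or < 0.5 × LLN (central laboratory ranges) that was not present at screening*. The sponsor should confirm the low-side multiple. Half of LLN can be reached from every normal baseline, by a fall of more than 50% from 1.0 × LLN, 66.7% from 1.5, 75% from 2.0 and 80% from 2.5.
2. Amend the lead sentence of Section 5.2.1 to: *within the first 4 weeks (criterion 4: at any post-dose visit)*. Without this the contradiction stays in the text.
3. Leave the stopping rule at 4 weeks and grade 3 or higher.
4. Copy the definition into the SAP for the DLT tables.

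The cost is wording in two documents, with no extra draw. Some more values would be flagged: low values from baselines below 2.5 × LLN, and high values between 2 × ULN and baseline + 2 × ULN. In the other direction, the present and proposed low-side limits coincide where B − 2 = 0.5, that is at B = 2.5. Above that, some falls that now qualify would drop out, for example 3.0 to 0.9 × LLN. A value such as 0.9 × LLN would still be marked low in the listings and shift tables.

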9.5 Monitoring of Adverse events

The investigator(s) will monitor their participants for the occurrence of adverse events during the course of the study and record all observed adverse events in the case report form.

Adverse Events regardless of seriousness or relationship to study drug, including those

occurring during the Screening period (where applicable), are to be recorded in the CRF. Whenever possible, symptoms should be grouped as a single syndrome or diagnosis. The Investigator should specify the date of onset, maximal intensity, corrective therapy given, outcome, and his/her opinion as to whether there is a reasonable possibility that the Adverse Event was caused by the study drug.

Any adverse events that meet the 4 criteria under Stopping Rules (Section 5.2.1) must be communicated to the sponsor (or designee) within 24 hours of first knowledge of such event

The investigator must provide the sponsor appropriate information concerning any findings suggesting significant hazards, contraindications, side effects or precautions pertinent to the safety of the study drug. The investigator will instruct participants prior to administration of study drug to report any physical changes or new symptoms that they notice during the course of the study. The investigator must report all serious adverse events (defined above) within 24 hours of their onset to Ion Channel Innovations, LLC.:

[REDACTED] M.D.

[name]

[name]

[contact]

[contact]

In case of prolongation of $QT_cF \geq 500$ ms, or an increase in $QT_cF \geq 60$ ms from baseline, a blood sample should be drawn for measurement of serum potassium, calcium, magnesium, and *hSlo* cDNA.

A cardiologist should be consulted, and the participant should continue to have his ECG monitored until the ECG abnormality resolves or becomes stable.

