Microscopic RBC (exception is urine sample post-catherization)	6 – 10 RBC/hpf	>10 RBC/hpf	Gross hematuria	-
CARDIOVASCULAR				
Hypertension	Asymptomatic, transient (<24 H) increase by >20 mmHg (diastolic) or >150/100 if previously WNL; not requiring treatment	Recurrent or persistent (>24H) or symptomatic increase by >20 mmHg (diastolic) or to >150/100 if previously WNL; may require monotherapy	Requiring more than one drug or more intensive therapy than previously	Life-threatening consequences (e.g., hypertensive crisis)
Hypotension	Transient orthostatic hypotension, intervention not indicated	Symptoms corrected with oral fluid replacement	IV fluid required; hospitalization not required	Hospitalization required
Conduction abnormality/ atrioventricular heart block	Asymptomatic, no intervention indicated	Non-urgent medical intervention indicated	Symptomatic & incompletely controlled medically or controlled with device (e.g., pacemaker)	Life-threatening
Prolonged QTc interval	Asymptomatic, QTc interval 0.43 – 0.48 sec	Asymptomatic, QTc interval >0.48 sec	Symptomatic	Life-threatening (e.g., arrhythmia associated with CHF, hypotension, syncope, shock)
Supraventricular & nodal arrhythmia	Asymptomatic, no intervention indicated	Symptomatic, but not requiring treatment	Symptomatic & incompletely controlled medically or controlled with device (e.g., pacemaker)	Life-threatening (e.g., arrhythmia associated with CHF, hypotension, syncope, shock)
Ventricular arrhythmia	Asymptomatic, intervention not indicated	Symptomatic, but not requiring treatment	Symptomatic & incompletely controlled medically or controlled with device (e.g., pacemaker)	Life-threatening (e.g., arrhythmia associated with CHF, hypotension, syncope shock)
Cardiac Arrhythmia – Other	Asymptomatic, not requiring treatment	Symptomatic, but not requiring treatment	Symptomatic, and requiring treatment of underlying cause	Life-threatening (e.g., arrhythmia associated with CHF, hypotension, syncope, shock)
Cardiac ischemia/infarction	Asymptomatic arterial narrowing without ischemia	Asymptomatic and testing suggests ischemia	Asymptomatic ischemia (angina) or testing consistent with ischemia, intervention indicated	Acute myocardial infarction

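### No asymptomatic QTc value, however long, can trigger the Protocol 5.2.1 stopping rule, so a QTcF of 500 ms or more does not bring the mandatory halt and outside review

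*Protocol*

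**What the plan says.** **Stopping rule (Protocol 5.2.1).** Within 4 weeks of the single administration, "if any participant experiences a grade 3 or higher dose limiting toxicity, no additional participants will be accrued" and no more doses of active drug or placebo are given. The way back is fixed: "After review of these data with EC and MOH the clinical study may resume only with concurrence of EC and MOH".

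**DLT definition (Protocol 5.2.1, criterion 1).** "Any adverse events of Grade 2 or higher in the cardiovascular category of adverse event criteria listed in" Appendix A counts as a DLT. DLT status thus starts at Grade 2, and stopping starts at Grade 3.

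**QTc grades (Appendix A, Cardiovascular).** Grade 1 is "Asymptomatic, QTc interval 0.43 – 0.48 sec". Grade 2 is "Asymptomatic, QTc interval >0.48 sec". Grade 3 is defined only by the presence of symptoms, and Grade 4 only by danger to life. Neither carries a value in seconds. The row does not say which QT correction applies.

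**Action level (Protocol 9.5).** A QTcF of 500 ms or more, or a rise of 60 ms or more from baseline, calls for a blood sample (potassium, calcium, magnesium and *hSlo* cDNA). In addition, "A cardiologist should be consulted, and the participant should continue to have his ECG monitored until the ECG abnormality resolves or becomes stable". Nothing is said there about holding enrollment or dosing.

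**Reporting (Protocol 9.5).** "Any adverse events that meet the 4 criteria under Stopping Rules (Section 5.2.1) must be communicated to the sponsor (or designee) within 24 hours". The four criteria are the DLT criteria, although this sentence calls them stopping rules. Serious adverse events are also reported within 24 hours.

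**Separate pause (Protocol 5.2).** "If a clinically serious sign or symptom is reported the medical monitor will contact the sponsor and no further enrollment will be done". Either the medical monitor or the sponsor can end this pause.

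**The concern.** The protocol has three rules for a long QTc: an action level in 9.5, a DLT grade in Appendix A and a stopping threshold in 5.2.1. They do not meet. The level at which the protocol asks for a cardiologist lies inside a grade that cannot stop the trial, and that grade has no ceiling.

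Protocol 2.0 makes safety the primary objective. Section 5.2.1 names increased potassium efflux as the source of potential toxicity, and 12-lead ECGs are taken at every visit. Those inside the 4-week window (1 and 2 hours after dosing, week 1 and week 4) could detect a marked prolongation. The stopping rule is the only provision that halts dosing until bodies outside the sponsor agree to resume, and an asymptomatic ECG finding of this kind cannot reach it.

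A smaller issue is that Appendix A takes no account of change from baseline. The DLT count, which SAP 9.4 tabulates, can therefore leave out a larger QTcF rise and include a smaller one.

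**Working it through.** The plan gives no figure to reproduce. The check applies the written thresholds to QTc values in whole milliseconds.

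**Which scale governs.** Protocol 9.4 says that events listed in Appendix A take its grades; the general severity scale is for unlisted events. Prolonged QTc is listed, so Appendix A decides. Grade 4 does not offer a way round: its examples are clinical events such as syncope or shock, and the note in Protocol 9.2 limits life-threatening to actual risk of death at the time.

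**Step 1: absolute value, no symptoms.** Grade 1 = 430 to 480 ms; Grade 2 = above 480 ms; DLT if grade ≥ 2; stop if grade ≥ 3.

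| QTc (ms) | Grade | DLT | Stopping rule | 9.5 level of 500 ms (QTcF) |
|---|---|---|---|---|
| 480 | 1 | no | no | no |
| 481 | 2 | yes | no | no |
| 500 | 2 | yes | no | yes |
| 550 | 2 | yes | no | yes |
| 600 | 2 | yes | no | yes |

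Over all values from 300 to 800 ms the highest grade is 2, so the rule is never met.

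**Step 2: other Grade 3 entries.** In the Chemistries block of Appendix A, BUN of 41–50 mg/dL and potassium of 2.5 to <3.0 mEq/L are Grade 3 on the number alone, under the column headed severe. Under DLT criterion 2 they are Grade 3 DLTs and halt the trial without symptoms. Stopping is therefore not reserved for symptomatic events in general.

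**Step 3: change from baseline, no symptoms.** The largest rise that stays out of the DLT definition is 480 − baseline.

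| Baseline (ms) | Largest rise that is not a DLT (ms) | Rises that meet the 9.5 level but are not a DLT |
|---|---|---|
| 370 | 480 − 370 = 110 | 60 to 110 |
| 400 | 480 − 400 = 80 | 60 to 80 |
| 420 | 480 − 420 = 60 | 60 only |
| 421 | 480 − 421 = 59 | none |

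The gap exists for every baseline of 420 ms or less. It can also reverse the order of two men:
- 400 to 478 ms: rise 478 − 400 = 78 ms, action level met, Grade 1, not a DLT.
- 440 to 482 ms: rise 482 − 440 = 42 ms, action level not met, Grade 2, a DLT.

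**Step 4: what still applies at an asymptomatic 500 ms.** Grade 2 makes it a DLT, so the sponsor hears within 24 hours. The 5.2 pause applies if the finding is judged a clinically serious sign. That section names no QTc level, speaks of enrollment rather than of men enrolled but not yet dosed, and lets the medical monitor or sponsor lift the pause.

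**The case against.** **Dosing is not simply left open.** A reader might infer that the trial carries on regardless after a QTcF of 500 ms. The documents do not support that. Section 5.2 covers signs as well as symptoms, and once a sign is classed as clinically serious the pause is mandatory. With one dose per man, a pause in enrollment prevents most new exposure. This objection stands. What remains is narrower: there is no defined QTc trigger, no EC or MOH agreement is needed, and men already enrolled are not mentioned.

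**Symptomatic cases are covered.** It is tempting to say that any 60 ms rise ending at 480 ms or below escapes the DLT definition. Symptomatic prolongation is Grade 3 at any value and stops the trial, so the point is confined to asymptomatic men.

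**Smaller rises can still be reported quickly.** Protocol 9.2 lets the investigator class an important medical event as serious, and one of its examples is an asymptomatic ALT rise. A QTcF rise needing a cardiologist could qualify for 24-hour reporting, but only by judgement.

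**The grading may be deliberate.** The arrhythmia rows of Appendix A also keep Grade 3 for symptomatic events. That is fair, but the block is not uniform: the ischemia row admits asymptomatic ischemia or a test result where intervention is indicated, and the hypertension row turns on treatment. Nothing explains why the 9.5 action level should have no counterpart in the stopping rule.

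**A management trigger and a toxicity grade need not coincide, and the data are not lost.** SAP 9.4 presents ECG change from baseline at each post-dose visit, with shift tables, and SAP 9.2 lists QTcF. This largely stands and makes the 60 ms issue secondary.

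**No cardiac signal is reported.** Protocol 1.5 describes no cardiac toxicity in animals. Section 5.2 cites 20 men given up to 16000 µg, with one possibly related event, which was not cardiac. This also stands: the point concerns a risk the protocol chose to monitor, not an expected effect.

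**Conclusion.** The point holds for asymptomatic participants. No QTc value reaches Grade 3, so a QTcF at or above the protocol's own 500 ms action level is a DLT reported within 24 hours but cannot bring the mandatory halt with EC and MOH agreement. The only hold is the judgement-based 5.2 pause. This follows from the written grades and needs no assumption about event rates.

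The secondary point holds for asymptomatic rises of 60 ms or more ending at 480 ms or below, from baselines of 420 ms or less. They meet the action level, are at most Grade 1, and fall outside the DLT-based 24-hour report unless the investigator judges them serious.

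A reader might go on to estimate how many men an earlier stop would keep from being dosed. The documents give no rate for such an event, and 5.2.1 allows dosing to resume after review, so no such number can be supported. No efficacy test, estimate or error rate is affected. The gap is in safety monitoring, and it is worth closing because the correction is small.

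**What to change.** **Appendix A, QTc row.** Name QTcF as the measure, as 9.5 does.
- Grade 2: asymptomatic with QTcF above 480 and below 500 ms, or a rise of at least 60 ms over the pre-dose Visit 2 value.
- Grade 3: symptomatic, or QTcF of 500 ms or more confirmed by the central over-reader.
- State that the highest grade met applies, so that a value cannot sit in two grades.

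**Protocol 5.2.** Apply the enrollment pause while the over-read of a QTcF of 500 ms or more is awaited, and say that it includes men enrolled but not yet dosed. The over-read can take up to 48 hours (Protocol 6.4).

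**Protocol 9.5.** Refer to the four DLT criteria instead of calling them stopping rules.

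**Check of the revised grades, no symptoms.** 440 to 500 ms becomes Grade 3 and stops. 400 to 478 ms (+78) becomes Grade 2, a reported DLT. 440 to 482 ms (+42) and 450 to 490 ms (+40) stay Grade 2. The DLT table in SAP 9.4 follows without further change.

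**Cost.** One table row, a sentence in 5.2 and a phrase in 9.5. There is no new procedure, because QTcF is already measured and over-read. The downside is a possible temporary halt for a QTcF of 500 ms or more unrelated to treatment; requiring over-read confirmation reduces that risk.
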